7.3.6 Percent BSA Affected

The % BSA recorded at Visit 1, 2, and 3 will be summarized descriptively by cohort and visit.

All data will be listed by cohort and patient.

NOVUM PHARMACEUTICAL RESEARCH SERVICES
STATISTICAL ANALYSIS PLAN

Desoximetasone 0.15% Topical Spray

Protocol / Study No. DSXS 1502a / 71615002

7.3.7 Application Site Reaction

A frequency summary table comparing application site reaction for each cohort will be presented by visit.

All data will be listed by cohort and patient.

7.3.8 Pruritus Assessment

A frequency summary table comparing the severity of pruritus for each cohort will be presented by visit.

All data will be listed by cohort and patient.

7.4 Multiple Comparisons

No multiple comparison adjustment will be made in this study.

7.5 Methods for Handling Missing Data

For demographic and baseline characteristics, each variable will be analyzed using all available data. Patients with missing data will be excluded only from analyses for which data are not available.

7.6 Interim Analyses

There is no interim analysis planned in this study.

7.7 Changes to the Planned Analyses

Protocol Section 10.1.3 states as a secondary analysis of the data a logistic regression of the proportion of patients in the study with HPA axis suppression will be performed with %BSA affected as a covariate. The following will be applied during the analyses.

As a secondary analysis of the data a logistic regression of the proportion of patients in the study with HPA axis suppression may be performed with %BSA affected as a covariate. This will depend on the distribution of the %BSA data collected.

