### 7.3 Scientific and Statistical Considerations

In some instances high potency steroids applied topically have been known to cause suppression of the hypothalamic-pituitary-adrenal (HPA) axis. In order to assess HPA axis function plasma levels of cortisol are measured before (basal) and after a bolus administration of synthetic  $\alpha$  1-24-adrenocorticotropic hormone (ACTH). In this study CortrosynTM (cosyntropin, a synthetic subunit of ACTH) (Amphstar Pharmaceuticals, Inc.) will be used according to manufacturer instructions to assess HPA axis function (See Appendices E, F). Recovery from steroid-induced adrenal insufficiency is usually rapid after the treatment is withdrawn. See Appendix E for further explanation of the evaluation of the role of topical corticosteroids in HPA axis suppression.

Taro Pharmaceuticals USA has recently completed an open label safety and efficacy study to assess adrenal suppression in adults with moderate to severe plaque psoriasis after 4 weeks of treatment under maximal use conditions with the test product, desoximetasone 0.25% spray. Of 21 evaluable subjects, adrenal suppression was identified in 1 of 12 subjects having involvement of 10-15% of body surface area (BSA) and 2 of 9 subjects having involvement of >15% of BSA after treatment with Topicort® Topical Spray twice a day for 28 days. Adrenal function returned to normal at the first follow-up visit, which was 28 days after the end of treatment, for all 3 of these patients

This study design is based on similar studies performed, submitted and accepted by the FDA for recently approved high potency spray and foam topical corticosteroid formulations, topical corticosteroid/topical vitamin D3 analogue combination agents, and recommendations from the FDA in IND 101789 Guidance Meeting that took place on 01/14/2015 and an FDA Advice Letter dated 04/27/2015.

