## **CONFIDENTIAL PROTOCOL**

An Open Label, Safety Study to Assess the Potential for Adrenal Suppression Following Treatment with Desoximetasone 0.15% Topical Spray (Taro Pharmaceuticals U.S.A., Inc.) in Patients with Atopic Dermatitis

---

from a post-treatment cortisol response test will be included in the analysis. Patients who have not used 42 doses of the study drug will be excluded from the primary analysis of HPA axis suppression.

The primary analysis of interest is the proportion of patients in each group who are considered to have demonstrated possible HPA axis suppression following treatment with the study medication. As a secondary analysis of the data a logistic regression of the proportion of patients in the study with HPA axis suppression will be performed with %BSA affected as a covariate. See Appendix E for results from the cortisol response test considered indicative of potential HPA axis suppression.

The study will be enrolled by Cohort starting with Cohort 1 and each cohort will be reviewed for the potential of HPA axis suppression. If at least 50% of patients in Cohort 1 experience HPA axis suppression once the minimum number of patients has been enrolled and completed the cohort, enrollment for that cohort will be stopped and no further cohorts will be initiated. If at least 35% of patients have experienced HPA axis suppression across cohorts combined during the study, enrollment will be discontinued and no other cohorts will be initiated. Cohort 2 will not begin until safety data has been reviewed for Cohort 1. The same process will be followed for each Cohort until the study is complete.

For all patients the actual amount of desoximetasone (mg) applied during the study will be calculated from recorded bottle weights and presented.

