7.2 Safety Analysis of Potential HPA Axis Suppression

Dosing will be twice a day for 28 days excluding the doses prior to the Cortisol Response Test (54 applications). All patients who are enrolled, use at least 42 doses of the study drug and have data from a post-treatment cortisol response test will be included in the analysis. Patients who have not used 42 doses of the study drug will be excluded from the primary analysis of HPA axis suppression.

The primary analysis of interest is the proportion of patients in each group who are considered to have demonstrated possible HPA axis suppression following treatment with the study medication. As a secondary analysis of the data a logistic regression of the proportion of patients in the study with HPA axis suppression may be performed with %BSA affected as a covariate. This will depend on the distribution of the %BSA data collected.

The study will be enrolled by Cohort starting with Cohort 1 and each cohort will be reviewed for the potential of HPA axis suppression. If at least 50% of patients in Cohort 1 experience HPA axis suppression once the minimum number of patients has been enrolled and completed the cohort, enrollment for that cohort will be stopped and no further cohorts will be initiated. If at least 35% of patients have experienced HPA axis suppression across cohorts combined during the study, enrollment will be discontinued and no other cohorts will be initiated. Cohort 2 will not begin until safety data has been reviewed for Cohort 1. The same process will be followed for each Cohort until the study is complete.

For all patients the actual amount of desoximetasone (mg) applied during the study will be

NOVUM PHARMACEUTICAL RESEARCH SERVICES
STATISTICAL ANALYSIS PLAN

Desoximetasone 0.15% Topical Spray

Protocol / Study No. DSXS 1502a / 71615002

calculated from recorded bottle weights and presented.

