| | | Randomized | Included | Randomized | Included | Randomized | Included | Randomized | Included | Randomized | Included |
| All | - | xx | xx(xx.x%) | xx | xx(xx.x%) | xx | xx(xx.x%) | xx | xx(xx.x%) | xx | xx(xx.x%) |
| xx | xxxx | xx | xx (xx.x%) | xx | xx(xx.x%) | xx | xx(xx.x%) | xx | xx(xx.x%) | xx | xx(xx.x%) |
| xx | xxxx | xx | xx(xx.x%) | xx | xx(xx.x%) | xx | xx(xx.x%) | xx | xx(xx.x%) | xx | xx(xx.x%) |

Created on: ddmmmyy hh:mm

Page 1 of N

T16.1.9.5 Summary of Frequency of HPA Axis Suppression at the End of Treatment (Day 28)

| HPA Axis Suppression | All N=xx | Cohort 1 N=xx | Cohort 2 N=xx | Cohort 3 N=xx | Cohort 4 N=xx |
|----------------------|-------------|------------------|------------------|------------------|------------------|
| Yes | xx (xx.x%) | xx (xx.x%) | xx (xx.x%) | xx (xx.x%) | xx (xx.x%) |
| No | xx (xx.x%) | xx (xx.x%) | xx (xx.x%) | xx (xx.x%) | xx (xx.x%) |

Created on: ddmmmyy hh:mm

Page 1 of N

T16.1.9.5a Summary of Logistic Regression Analysis Results of HPA Axis Suppression at the End of Treatment (Day 28)

| | Odds Ratio | 95% Wald Confidence Limits | Wald Chi-Square | P-value |
|-------------------------|------------|-------------------------------|--------------------|---------|
| Cohort 1 vs. Cohort 2 | x.XXXX | x.XXXX, x.XXXX | x.XXXX | x.XXXX |
| Cohort 1 vs. Cohort 3 | x.XXXX | x.XXXX, x.XXXX | x.XXXX | x.XXXX |
| Cohort 1 vs. Cohort 4 | x.XXXX | x.XXXX, x.XXXX | x.XXXX | x.XXXX |
| Cohort 2 vs. Cohort 3 | x.XXXX | x.XXXX, x.XXXX | x.XXXX | x.XXXX |
| Cohort 2 vs. Cohort 4 | x.XXXX | x.XXXX, x.XXXX | x.XXXX | x.XXXX |
| Cohort 3 vs. Cohort 4 | x.XXXX | x.XXXX, x.XXXX | x.XXXX | x.XXXX |
| Baseline % BSA affected | x.XXXX | x.XXXX, x.XXXX | x.XXXX | x.XXXX |

Created on: ddmmmyy hh:mm

Page 1 of N

**T16.1.9.6 Summary of Percent BSA Affected with Atopic Dermatitis
(Safety Population)**

| Visit | Statistic | Cohort 1 (N = xx) | Cohort 2 (N = xx) | Cohort 3 (N = xx) | Cohort 4 (N = xx) |
|-------|---------------|----------------------|----------------------|----------------------|----------------------|
| 1 | n | xx | xx | xx | xx |
| | Mean \pm SD | xxx.x \pm xxx.x | xxx.x \pm xxx.x | xxx.x \pm xx.x | xxx.x \pm xxx.x |
| | Median | xxx.x | xxx.x | xxx.x | xxx.x |
| | Range | xxx.x – xxx.x | xxx.x – xxx.x | xxx.x – xxx.x | xxx.x – xxx.x |
| 2 | | | | | |
| 3 | | | | | |

Created on: ddmmmyy hh:mm

Page 1 of N

**T16.1.9.7 Summary of Frequency of Investigator Global Assessment (IGA)
(Safety Population)**

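### Shell T16.1.9.5a adds cohort odds ratios that no analysis text names and that often have no finite estimate, and SAP 7.7 makes the regression optional on an undefined criterion

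*SAP*

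**What the plan says.** Protocol 10.1.3 states the secondary analysis without condition: a "logistic regression of the proportion of patients in the study with HPA axis suppression will be performed with %BSA affected as a covariate". The Protocol synopsis agrees. The synopsis and SAP 6 each list one secondary outcome measure, suppression at end of treatment with %BSA as covariate.

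SAP 7.2 weakens the commitment: a "logistic regression of the proportion of patients in the study with HPA axis suppression may be performed with %BSA affected as a covariate". SAP 7.7 declares this change and gives the condition: "This will depend on the distribution of the %BSA data collected". Neither section says which distribution would allow or block the analysis, and neither mentions the number of suppressed patients. Neither names cohort as a model term.

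Shell T16.1.9.5a in SAP 8 has the columns "Odds Ratio | 95% Wald Confidence Limits | Wald Chi-Square | P-value". Its rows are six pairwise cohort comparisons, starting with "Cohort 1 vs. Cohort 2", and one row for baseline %BSA. No exact, penalised or other sparse-data method is named anywhere. SAP 8 cautions that the shells may not match every aspect of the study and can be modified. SAP 7.4 makes no multiplicity adjustment.

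**The concern.** There are two separate defects.

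First, the text and the shell describe different models. The text has one slope. The shell has four (three for cohort, one for %BSA), in 25 to 50 patients with few expected events. A cohort with no suppressed patient has no finite maximum-likelihood log odds ratio against any other cohort. Software would still typically print an extreme odds ratio, a huge standard error and a Wald p-value near 1, which a reader could take as evidence of no age effect. For a paediatric adrenal-safety study moving to ever younger cohorts, that misreading matters.

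Second, the run-or-drop condition has no threshold. The study is open label and suppression is reviewed cohort by cohort, so the decision can be taken with the outcomes in view. The condition also ignores the number of events, which largely determines whether the fit is informative.

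**Working it through.** **Plan's own figures.** The totals of 25 and 50 reproduce as cohort sums: 10+5+5+5 and 20+10+10+10. The 35 in Protocol 10.1.1 and SAP 5 has no stated rate, precision or power behind it and cannot be reproduced.

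**Inputs.**
- Cohort sizes: 10–20, 5–10, 5–10 and 5–10 (SAP 4). For N=35 a 14/7/7/7 split is assumed.
- Rate: the only one in the documents is in Protocol 7.3, where "adrenal suppression was identified in 1 of 12 subjects having involvement of 10-15% of body surface area (BSA) and 2 of 9 subjects" with more than 15% involvement. Pooled, 3/21 = 14.3% (exact 95% CI 3.0% to 36.3%). Those were adults with psoriasis on the 0.25% spray, so applying the rate p equally to all four cohorts is an assumption.

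**Step 1: events per slope.** Expected events are N × p, or 3.6, 5.0 and 7.1 at N = 25, 35 and 50. Divided by four slopes, that is 0.9, 1.25 and 1.8.

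**Step 2: rows lost.** With m cohorts that have no events, 6 − C(4−m, 2) of the six odds ratios are lost: 3 for m=1, 5 for m=2, 6 for m≥3.

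**Step 3: chance of at least one all-No or all-Yes cohort.** P = 1 − ∏[1 − (1−p)^n − p^n]. At p = 1/7 the p^n term is negligible:
- N=25: 1 − (1 − 0.2141)(1 − 0.4627)³ = 0.878
- N=35: 1 − (1 − 0.1155)(1 − 0.3399)³ = 0.746
- N=50: 1 − (1 − 0.0458)(1 − 0.2141)³ = 0.537

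| Assumed rate | N=25 | N=35 | N=50 |
|---|---|---|---|
| 10% | 96% | 89% | 76% |
| 14.3% | 88% | 75% | 54% |
| 20% | 73% | 53% | 30% |
| 30% | 45% | 23% | 8% |

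At 14.3% the mean number of odds ratios lost is 3.9, 2.9 and 1.9 of six. A zero-event cohort is the majority outcome only when the rate is below about 27.8% (N=25), 20.8% (N=35) or 15.0% (N=50).

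**Step 4: stopping rules.** The table assumes all four cohorts enrol. Applying the 50% and 35% rules once after each cohort, and counting unenrolled cohorts as lost, the chance that at least one cohort odds ratio is missing at a 30% rate is 79%, 68% and 61%. A high rate therefore does not rescue the six rows.

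**Step 5: what the shell would print.** Take events of 3/1/1/0 in 14/7/7/7. Ordinary maximum likelihood returns a Cohort 4 versus Cohort 1 odds ratio of about 5×10⁻¹⁰ with a log-odds-ratio standard error of about 17,600. The Wald z is ln(5×10⁻¹⁰)/17,600 = −21.4/17,600 ≈ −0.001, so p ≈ 1. A Firth fit gives 0.21 with standard error 1.65, which is finite but very imprecise.

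**Step 6: the %BSA slope.** This was simulated with %BSA uniform on 10–30 (assumed), p = 14.3% and no stopping. Under the shell model the slope is non-finite in about 6–7%, 1.4% and 0.2% of trials at N = 25, 35 and 50. With %BSA alone it is about 3%, 0.7% and 0.1%.

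**The case against.** A reader might infer that the declared secondary outcome will usually be inestimable. The documents do not support that. The outcome is the %BSA effect, and Step 6 shows its slope is normally finite even under the shell model. The 88%, 75% and 54% figures concern only the cohort rows.

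It can be said that a shell is not a model and that SAP 8 allows shells to change. That is fair, and it makes this a mismatch to reconcile. It does not tell the programmer which model applies, and SAP 7.7, which lists departures from the protocol, does not mention the added factor.

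A reader might also infer that the SAP prescribes ordinary maximum likelihood. It does not name an estimator. That is inferred from the Wald headings and the absence of any alternative, and Wald limits can be computed from a penalised fit.

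Finally, the spread of %BSA is not irrelevant. Entry is limited to 10–30%, and a narrow spread would make the slope uninformative. The condition is declared openly, concerns a covariate, and sits in a SAP that must be final before database lock. It would go too far to say the plan is to drop the analysis according to its result. What stands is that the condition has no threshold, ignores events, and can be judged with outcomes known.

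**Conclusion.** The point holds as a text–shell mismatch combined with an undefined condition. If T16.1.9.5a is followed as drawn and no sparse-data method is used, at least three of its six cohort odds ratios have no finite estimate with probability 88% (N=25), 75% (N=35) and 54% (N=50) at a common 14.3% rate. Over assumed rates of 10% to 30% the ranges are 96% to 45%, 89% to 23% and 76% to 8%. It cannot be called the usual outcome at every plausible rate: at N=50 with all cohorts enrolled, it falls below one half above about 15%.

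The exposure is a misreading of the age rows. The %BSA estimate, though imprecise on so few events, is usually finite. The primary proportion, the cohort rates in T16.1.9.5 and the cortisol listing are untouched. The change is worth making before database lock, but it is not critical to the trial's main result.

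**What to change.** 1. Delete the six Wald cohort contrasts from T16.1.9.5a. Cohort rates are already in T16.1.9.5, where exact binomial limits can be added.
2. State one model in SAP 7.2: suppression on baseline %BSA alone, fitted by Firth-penalised or exact logistic regression with profile-penalised or exact limits. The analysis text does not say which visit's %BSA is meant, and %BSA is recorded at three visits, so baseline (the shell's choice) should be written in.
3. Replace the %BSA-distribution condition in SAP 7.2 and 7.7 with a rule fixed in advance. For example, fit whenever there is at least one suppressed and one non-suppressed patient, and label the result descriptive below a stated number of events, because a fit on one or two events says almost nothing.

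The cost is SAP wording, one shell edit and an option in the SAS logistic procedure. The downside is slight shrinkage of the %BSA estimate and no adjusted cohort odds ratios. With %BSA alone, separation is already rare, so the penalised or exact fit is a safeguard. Removing the cohort contrasts and fixing the rule do most of the work.

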8. TABLE, LISTING AND FIGURE SHELLS

The following shells are provided in order to provide a framework for the display of data from this study. These shells may not be reflective of every aspect of this study but are intended to show the general layout of the Tables, Listings and Figures that will be included in the final

NOVUM PHARMACEUTICAL RESEARCH SERVICES
STATISTICAL ANALYSIS PLAN

Desoximetasone 0.15% Topical Spray

Protocol / Study No. DSXS 1502a / 71615002

clinical study report. Tables, Listings and Figures are numbered following the ICH structure. Table headers, variables names and footnotes will be modified as needed following data analyses. All descriptive and inferential statistical analyses will be performed using SAS® statistical software Version 9.4 or higher, unless otherwise noted.

TABLE, LISTING AND FIGURE SHELLS

T16.1.9.1 Summary of Enrolled Patients

| Patients | Cohort 1 | Cohort 2 | Cohort 3 | Cohort 4 | Total |
|-------------------|-----------------|-----------------|-----------------|-----------------|--------------|
| Screened | | | | | xxx |
| Randomized | xxx | xxx | xxx | xxx | xxx |
| Completed Study | xxx | xxx | xxx | xxx | xxx |
| Terminated Early | xxx | xxx | xxx | xxx | xxx |
| Adverse Event | xxx | xxx | xxx | xxx | xxx |
| Enrolled in error | xxx | xxx | xxx | xxx | xxx |
| Lack of efficacy | xxx | xxx | xxx | xxx | xxx |
| Lost to follow-up | xxx | xxx | xxx | xxx | xxx |
| etc. | | | | | |
| Other | xxx | xxx | xxx | xxx | xxx |

Created on: ddmmmyy hh:mm

Page 1 of N

**T16.1.9.2 Summary of Protocol Deviations
(Safety Population)**

| | Cohort 1 | Cohort 2 | Cohort 3 | Cohort 4 | Total |
|---|----------|----------|----------|----------|-------|
| Total Patients with Protocol Deviations | xxx | xxx | xxx | xxx | xxx |
| Total Deviations | xxx | xxx | xxx | xxx | xxx |
| Enrolled in Error | xxx | xxx | xxx | xxx | xxx |
| Lost to Follow-up | xxx | xxx | xxx | xxx | xxx |
| Missed Visit | xxx | xxx | xxx | xxx | xxx |
| Non-compliance with study drug | xxx | xxx | xxx | xxx | xxx |
| Outside Visit Window | xxx | xxx | xxx | xxx | xxx |
| Restricted Medication Use | xxx | xxx | xxx | xxx | xxx |
| etc | | | | | |
| Other | xxx | xxx | xxx | xxx | xxx |

Created on: ddmmmyy hh:mm

Page 1 of N

**T16.1.9.3 Summary of Demographic Data
(Safety Population)**

| | | Cohort 1 | Cohort 2 | Cohort 3 | Cohort 4 | Total | P-value |
|-------------|---|------------|------------|------------|------------|------------|----------------|
| | | N=xx | N=xx | N=xx | N=xx | N=xx | |
| Age (years) | n | xx | xx | xx | xx | xx | x.XXXX |
| | Mean ± SD | xx.x ± x.x | |
| | Median | xx.x | xx.x | xx.x | xx.x | xx.x | |
| | Range | xx-xx | xx-xx | xx-xx | xx-xx | xx-xx | |
| Age Groups | <=1 | - | - | - | xx (xx.x%) | - | |
| | 2 – 5 | - | - | xx (xx.x%) | - | - | |
| | 6 – 11 | - | xx (xx.x%) | - | - | - | |
| | 12 – 17 | xx (xx.x%) | - | - | - | - | |
| | 18 – 40 | - | - | - | - | - | |
| | 41 – 64 | - | - | - | - | - | |
| | 65 – 75 | - | - | - | - | - | |
| | > 75 | - | - | - | - | - | |
| Race | American Indian or Alaska Native | xx (xx.x%) | x.XXXX |
| | Asian | xx (xx.x%) | |
| | Black/African American | xx (xx.x%) | |
| | Native Hawaiian or other Pacific Islander | xx (xx.x%) | |
| | White | xx (xx.x%) | |
| | Other | xx (xx.x%) | |
| Ethnicity | Hispanic or Latino | xx (xx.x%) | x.XXXX |
| | Not Hispanic or Latino | xx (xx.x%) | |

N= number of patients in the cohort; n= number of patients with data available; % is based on N

**T16.1.9.3 Summary of Demographic Data
(Safety Population)**

| | n | Cohort 1 | Cohort 2 | Cohort 3 | Cohort 4 | Total | P-value |
|--------------------|--------------|------------|------------|------------|------------|------------|---------|
| | | N=xx | N=xx | N=xx | N=xx | N=xx | |
| Baseline Total BSA | n | xx | xx | xx | xx | xx | x.XXXX |
| | Mean ± SD | xx.x ± x.x | |
| | Median | xx.x | xx.x | xx.x | xx.x | xx.x | |
| | Range | xx-xx | xx-xx | xx-xx | xx-xx | xx-xx | |
| Baseline IGA | Clear | xx (xx.x%) | x.XXXX |
| | Almost Clear | xx (xx.x%) | |
| | Mild | xx (xx.x%) | |
| | Moderate | xx (xx.x%) | |
| | Severe | xx (xx.x%) | |
| EASI | n | xx | xx | xx | xx | xx | x.XXXX |
| | Mean ± SD | xx.x ± x.x | |
| | Median | xx.x | xx.x | xx.x | xx.x | xx.x | |
| | Range | xx-xx | xx-xx | xx-xx | xx-xx | xx-xx | |

N= number of patients in the cohort; n= number of patients with data available; % is based on N

T16.1.9.4 Summary of Patients Randomized, Included in Safety Analysis of Potential HPA Axis Suppression by Study Center

| Site No. | PI Name | Total | | Cohort 1 | | Cohort 2 | | Cohort 3 | | Cohort 4 | |
|----------|---------|------------|------------|------------|-----------|------------|-----------|------------|-----------|------------|-----------|
| | | Randomized | Included | Randomized | Included | Randomized | Included | Randomized | Included | Randomized | Included |
| All | - | xx | xx(xx.x%) | xx | xx(xx.x%) | xx | xx(xx.x%) | xx | xx(xx.x%) | xx | xx(xx.x%) |
| xx | xxxx | xx | xx (xx.x%) | xx | xx(xx.x%) | xx | xx(xx.x%) | xx | xx(xx.x%) | xx | xx(xx.x%) |
| xx | xxxx | xx | xx(xx.x%) | xx | xx(xx.x%) | xx | xx(xx.x%) | xx | xx(xx.x%) | xx | xx(xx.x%) |

Created on: ddmmmyy hh:mm

Page 1 of N

T16.1.9.5 Summary of Frequency of HPA Axis Suppression at the End of Treatment (Day 28)

| HPA Axis Suppression | All N=xx | Cohort 1 N=xx | Cohort 2 N=xx | Cohort 3 N=xx | Cohort 4 N=xx |
|----------------------|-------------|------------------|------------------|------------------|------------------|
| Yes | xx (xx.x%) | xx (xx.x%) | xx (xx.x%) | xx (xx.x%) | xx (xx.x%) |
| No | xx (xx.x%) | xx (xx.x%) | xx (xx.x%) | xx (xx.x%) | xx (xx.x%) |

Created on: ddmmmyy hh:mm

Page 1 of N

T16.1.9.5a Summary of Logistic Regression Analysis Results of HPA Axis Suppression at the End of Treatment (Day 28)

| | Odds Ratio | 95% Wald Confidence Limits | Wald Chi-Square | P-value |
|-------------------------|------------|-------------------------------|--------------------|---------|
| Cohort 1 vs. Cohort 2 | x.XXXX | x.XXXX, x.XXXX | x.XXXX | x.XXXX |
| Cohort 1 vs. Cohort 3 | x.XXXX | x.XXXX, x.XXXX | x.XXXX | x.XXXX |
| Cohort 1 vs. Cohort 4 | x.XXXX | x.XXXX, x.XXXX | x.XXXX | x.XXXX |
| Cohort 2 vs. Cohort 3 | x.XXXX | x.XXXX, x.XXXX | x.XXXX | x.XXXX |
| Cohort 2 vs. Cohort 4 | x.XXXX | x.XXXX, x.XXXX | x.XXXX | x.XXXX |
| Cohort 3 vs. Cohort 4 | x.XXXX | x.XXXX, x.XXXX | x.XXXX | x.XXXX |
| Baseline % BSA affected | x.XXXX | x.XXXX, x.XXXX | x.XXXX | x.XXXX |

Created on: ddmmmyy hh:mm

Page 1 of N

**T16.1.9.6 Summary of Percent BSA Affected with Atopic Dermatitis
(Safety Population)**

| Visit | Statistic | Cohort 1 (N = xx) | Cohort 2 (N = xx) | Cohort 3 (N = xx) | Cohort 4 (N = xx) |
|-------|---------------|----------------------|----------------------|----------------------|----------------------|
| 1 | n | xx | xx | xx | xx |
| | Mean \pm SD | xxx.x \pm xxx.x | xxx.x \pm xxx.x | xxx.x \pm xx.x | xxx.x \pm xxx.x |
| | Median | xxx.x | xxx.x | xxx.x | xxx.x |
| | Range | xxx.x – xxx.x | xxx.x – xxx.x | xxx.x – xxx.x | xxx.x – xxx.x |
| 2 | | | | | |
| 3 | | | | | |

Created on: ddmmmyy hh:mm

Page 1 of N

**T16.1.9.7 Summary of Frequency of Investigator Global Assessment (IGA)
(Safety Population)**

| Visit | Score | Cohort 1 (N = xx) | Cohort 2 (N = xx) | Cohort 3 (N = xx) | Cohort 4 (N = xx) |
|-------|-------------------------|----------------------|----------------------|----------------------|----------------------|
| 1 | 0 (Clear) | xx (xx.x%) | xx (xx.x%) | xx (xx.x%) | xx (xx.x%) |
| | 1 (Almost Clear) | xx (xx.x%) | xx (xx.x%) | xx (xx.x%) | xx (xx.x%) |
| | 2 (Mild Disease) | xx (xx.x%) | xx (xx.x%) | xx (xx.x%) | xx (xx.x%) |
| | 3 (Moderate Disease) | xx (xx.x%) | xx (xx.x%) | xx (xx.x%) | xx (xx.x%) |
| | 4 (Severe Disease) | xx (xx.x%) | xx (xx.x%) | xx (xx.x%) | xx (xx.x%) |
| 2 | 0 (Clear) | xx (xx.x%) | xx (xx.x%) | xx (xx.x%) | xx (xx.x%) |
| | 1 (Almost Clear) | xx (xx.x%) | xx (xx.x%) | xx (xx.x%) | xx (xx.x%) |
| | 2 (Mild Disease) | xx (xx.x%) | xx (xx.x%) | xx (xx.x%) | xx (xx.x%) |
| | 3 (Moderate Disease) | xx (xx.x%) | xx (xx.x%) | xx (xx.x%) | xx (xx.x%) |
| | 4 (Severe Disease) | xx (xx.x%) | xx (xx.x%) | xx (xx.x%) | xx (xx.x%) |

3

Created on: ddmmmyy hh:mm

Page 1 of N

**T16.1.9.8 Summary of Total Score - Eczema Area and Severity Index (EASI)
(Safety Population)**

| Visit | Statistic | Cohort 1 (N = xx) | Cohort 2 (N = xx) | Cohort 3 (N = xx) | Cohort 4 (N = xx) |
|-------|---------------|----------------------|----------------------|----------------------|----------------------|
| 1 | n | xx | xx | xx | xx |
| | Mean \pm SD | xxx.x \pm xx.x | xxx.x \pm xx.x | xxx.x \pm xx.x | xxx.x \pm xx.x |
| | Median | xxx.x | xxx.x | xxx.x | xxx.x |
| | Range | xxx - xxx | xxx - xxx | xxx - xxx | xxx - xxx |
| 2 | | | | | |
| 3 | | | | | |

Created on: ddmmmyy hh:mm

Page 1 of N

**T16.1.9.9 Overall Summary of Adverse Events
(Safety Population)**

| Description | Cohort 1 | Cohort 2 | Cohort 3 | Cohort 4 | Total |
|---|-----------------|-----------------|-----------------|-----------------|--------------|
| | N=xx | N=xx | N=xx | N=xx | N=xx |
| Patients Randomized | xxx | xxx | xxx | xxx | xxx |
| Patients with at least one AE | xx (xx.x%) | xx (xx.x%) | xx (xx.x%) | xx (xx.x%) | xx (xx.x%) |
| Discontinued study drug due to above AE | xx (xx.x%) | xx (xx.x%) | xx (xx.x%) | xx (xx.x%) | xx (xx.x%) |
| | | | | | |
| AEs reported | xxx | xxx | xxx | xxx | xxx |
| Mild | xx (xx.x%) | xx (xx.x%) | xx (xx.x%) | xx (xx.x%) | xx (xx.x%) |
| Moderate | xx (xx.x%) | xx (xx.x%) | xx (xx.x%) | xx (xx.x%) | xx (xx.x%) |
| Severe | xx (xx.x%) | xx (xx.x%) | xx (xx.x%) | xx (xx.x%) | xx (xx.x%) |
| Not Related | xx (xx.x%) | xx (xx.x%) | xx (xx.x%) | xx (xx.x%) | xx (xx.x%) |
| Related | xx (xx.x%) | xx (xx.x%) | xx (xx.x%) | xx (xx.x%) | xx (xx.x%) |
| Death | xx (xx.x%) | xx (xx.x%) | xx (xx.x%) | xx (xx.x%) | xx (xx.x%) |
| Serious AE | xx (xx.x%) | xx (xx.x%) | xx (xx.x%) | xx (xx.x%) | xx (xx.x%) |

Related = Possible, Probable, Definite

Created on: ddmmmyy hh:mm

Page 1 of N

**T16.1.9.10.1 Summary of Frequency of All Adverse Events by Body System
(Safety Population)**

| Body System | MedDRA Term | Cohort | Events | Patients | Fisher's p-value |
|-------------------------------|-------------|-----------------|--------|------------|------------------|
| Patients with at least one AE | Total | Cohort 1 (N=xx) | xx | xx (xx.x%) | x.xxxx |
| | | Cohort 2 (N=xx) | xx | xx (xx.x%) | |
| | | Cohort 3 (N=xx) | xx | xx (xx.x%) | |
| | | Cohort 4 (N=xx) | xx | xx (xx.x%) | |
| Ear and labyrinth disorders | Ear pain | Cohort 1 (N=xx) | xx | xx (xx.x%) | x.xxxx |
| | | Cohort 2 (N=xx) | xx | xx (xx.x%) | |
| | | Cohort 3 (N=xx) | xx | xx (xx.x%) | |
| | | Cohort 4 (N=xx) | xx | xx (xx.x%) | |

N = Total number of patient in each cohort; Percentage is based on total number of patients.

Created on: ddmmmyy hh:mm

Page 1 of N

**T16.1.9.10.2 Summary of Frequency of All Adverse Events in $\geq 2\%$ of Patients by Body System
(Safety Population)**

**T16.1.9.11 Summary of Frequency of All Adverse Events by Severity
(Safety Population)**

| Body System | MedDRA Term | Cohort | Mild | Moderate | Severe |
|-------------------------------|--------------------|-----------------|-------------|-----------------|---------------|
| Patients with at least one AE | Total | Cohort 1 (N=xx) | xx (xx.x%) | xx (xx.x%) | xx (xx.x%) |
| | | Cohort 2 (N=xx) | xx (xx.x%) | xx (xx.x%) | xx (xx.x%) |
| | | Cohort 3 (N=xx) | xx (xx.x%) | xx (xx.x%) | xx (xx.x%) |
| | | Cohort 4 (N=xx) | xx (xx.x%) | xx (xx.x%) | xx (xx.x%) |
| Ear and labyrinth disorders | Ear pain | Cohort 1 (N=xx) | xx (xx.x%) | xx (xx.x%) | xx (xx.x%) |
| | | Cohort 2 (N=xx) | xx (xx.x%) | xx (xx.x%) | xx (xx.x%) |
| | | Cohort 3 (N=xx) | xx (xx.x%) | xx (xx.x%) | xx (xx.x%) |
| | | Cohort 4 (N=xx) | xx (xx.x%) | xx (xx.x%) | xx (xx.x%) |

N = Total number of events in each cohort; Percentage is based on total number of events.

Created on: ddmmmyy hh:mm

Page 1 of N

**T16.1.9.12 Summary of Frequency of All Adverse Events by Relationship
(Safety Population)**

| Body System | MedDRA Term | Cohort | Related | Not Related |
|-------------------------------|--------------------|-----------------|----------------|--------------------|
| Patients with at least one AE | Total | Cohort 1 (N=xx) | xx (xx.x%) | xx (xx.x%) |
| | | Cohort 2 (N=xx) | xx (xx.x%) | xx (xx.x%) |
| | | Cohort 3 (N=xx) | xx (xx.x%) | xx (xx.x%) |
| | | Cohort 4 (N=xx) | xx (xx.x%) | xx (xx.x%) |
| Ear and labyrinth disorders | Ear pain | Cohort 1 (N=xx) | xx (xx.x%) | xx (xx.x%) |
| | | Cohort 2 (N=xx) | xx (xx.x%) | xx (xx.x%) |
| | | Cohort 3 (N=xx) | xx (xx.x%) | xx (xx.x%) |
| | | Cohort 4 (N=xx) | xx (xx.x%) | xx (xx.x%) |

N = Total number of events in each cohort; Percentage is based on total number of events.

Related = Possible, Probable, Definite

Created on: ddmmmyy hh:mm

Page 1 of N

**T16.1.9.13 Summary of Frequency of Serious Adverse Events
(Safety Population)**

| Body System | MedDRA Term | Cohort 1 N=xx | Cohort 2 N=xx | Cohort 3 N=xx | Cohort 4 N=xx |
|--|------------------------|--------------------------|--------------------------|--------------------------|--------------------------|
| Injury, poisoning and procedural complications | Alcohol poisoning | xx | xx | xx | xx |

Created on: ddmmmyy hh:mm

Page 1 of N

**T16.1.9.14 Summary of Shift Analysis of Clinical Laboratory Assessments (Chemistry) from Baseline to Day 28
(Safety Population)**

Alanine Aminotransferase (U/L)

| | Cohort 1 (N=xx) | | | Cohort 2 (N=xx) | | | Cohort 3 (N=xx) | | | Cohort 4 (N=xx) | | |
|------------|--------------------|---------------|---------------|--------------------|---------------|---------------|--------------------|---------------|---------------|--------------------|---------------|---------------|
| Baseline-> | Low | Normal | High |
| Endpoint | xx (xx.x%) | xx (xx.x%) | xx (xx.x%) |
| Low | xx (xx.x%) | xx (xx.x%) | xx (xx.x%) |
| Normal | xx (xx.x%) | xx (xx.x%) | xx (xx.x%) |
| High | xx (xx.x%) | xx (xx.x%) | xx (xx.x%) |

Table will continue for other lab parameters.

Similar table will be created for T16.1.9.18.

**T16.1.9.15 Summary of Shift Analysis of Clinical Laboratory Assessments (Hematology) from Baseline to Day 28
(Safety Population)**

**T16.1.9.16 Summary of Frequency of Pruritis Assessment
(Safety Population)**

| Visit | Score | Cohort 1 (N = xx) | Cohort 2 (N = xx) | Cohort 3 (N = xx) | Cohort 4 (N = xx) |
|-------|----------|----------------------|----------------------|----------------------|----------------------|
| 1 | None | xx (xx.x%) | xx (xx.x%) | xx (xx.x%) | xx (xx.x%) |
| | Mild | xx (xx.x%) | xx (xx.x%) | xx (xx.x%) | xx (xx.x%) |
| | Moderate | xx (xx.x%) | xx (xx.x%) | xx (xx.x%) | xx (xx.x%) |
| | Severe | xx (xx.x%) | xx (xx.x%) | xx (xx.x%) | xx (xx.x%) |
| 2 | None | xx (xx.x%) | xx (xx.x%) | xx (xx.x%) | xx (xx.x%) |
| | Mild | xx (xx.x%) | xx (xx.x%) | xx (xx.x%) | xx (xx.x%) |
| | Moderate | xx (xx.x%) | xx (xx.x%) | xx (xx.x%) | xx (xx.x%) |
| | Severe | xx (xx.x%) | xx (xx.x%) | xx (xx.x%) | xx (xx.x%) |

3

Created on: ddmmmyy hh:mm

Page 1 of N

**T16.1.9.17 Summary of Application Site Reaction
(Safety Population)**

| Sign / Symptom | Visit | Statistic | Cohort 1 (N = xx) | Cohort 2 (N = xx) | Cohort 3 (N = xx) | Cohort 4 (N = xx) | |
|----------------|-------|-----------|----------------------|----------------------|----------------------|----------------------|--|
| Burning | 1 | Absent | xxx (xx.x%) | xxx (xx.x%) | xxx (xx.x%) | xxx (xx.x%) | |
| | | Mild | xxx (xx.x%) | xxx (xx.x%) | xxx (xx.x%) | xxx (xx.x%) | |
| | | Moderate | xxx (xx.x%) | xxx (xx.x%) | xxx (xx.x%) | xxx (xx.x%) | |
| | | Severe | xxx (xx.x%) | xxx (xx.x%) | xxx (xx.x%) | xxx (xx.x%) | |
| 2 | | | | | | | |
| 3 | | | | | | | |
| Erosion | | | | | | | |
| Erosion | | | | | | | |
| Edema | | | | | | | |
| Pain | | | | | | | |
| Itching | | | | | | | |
| Dryness | | | | | | | |

L16.2.1 Listing of Discontinued Patients

| Cohort | Patient Number | Discontinuation Reason |
|---------------|-----------------------|--|
| Cohort 1 | xx-XXXX xx-XXXX | Withdrawal by Subject Lost to Follow-up |

Cohort 2
Cohort 3
Cohort 4

Created on: ddmmmyy hh:mm

Page 1 of N

L16.2.2 Listing of Protocol Deviations

| Cohort | Patient Number | Event Description |
|---------------|-----------------------|--------------------------------|
| Cohort 1 | xx-xxxx | Outside Visit Window (Visit 3) |

Cohort 2
Cohort 3
Cohort 4

Created on: ddmmmyy hh:mm

Page 1 of N

L16.2.3 Patients Excluded from Safety Analysis of Potential HPA Axis Suppression

| Cohort | Patient Number | Exclusion Reason |
|---------------|-----------------------|---|
| Cohort 1 | xx-xxxx | Patient has not used 42 doses of the study drug |

Cohort 2
Cohort 3
Cohort 4

Created on: ddmmmyy hh:mm

Page 1 of N

L16.2.4.1 Listing of Demographic Data

| Cohort | Patient Number | Age | Gender | Ethnicity | Race |
|---------------|-----------------------|------------|---------------|------------------------|---------------------------|
| Cohort 1 | xx-xxxx | 11 | Female | Not Hispanic or Latino | Black or African American |

Cohort 2

Cohort 3

Cohort 4

Created on: ddmmmyy hh:mm

Page 1 of N

L16.2.4.2 Listing of Medical History

| Cohort | Patient Number | System | Diagnosis or Surgical Procedure | Start Date | End Date | Ongoing |
|---------------|-----------------------|---------------|--|-------------------|-----------------|----------------|
| Cohort 1 | xx-xxxx | Gynecologic | Menopause | yyyy-mm-dd | yyyy-mm-dd | |

Cohort 2

Cohort 3

Cohort 4

Created on: ddmmmyy hh:mm

Page 1 of N

L16.2.4.3 Listing of Concomitant Medication

| Cohort | Patient Number | Treatment Area | Medication | Dosage | Frequency | Route | Start/End Date | Indication |
|---------------|-----------------------|-----------------------|-------------------|---------------|------------------|--------------|----------------------------|-------------------|
| Cohort 1 | xx-xxxx | No | Lisinopril | 20 MG | QD | PO | yyyy-mm-dd / yyyy-mm-dd | Hypertension |

Cohort 2

Cohort 3

Cohort 4

Created on: ddmmmyy hh:mm

Page 1 of N

L16.2.5.1 Listing of Drug Administration

| Cohort | Patient Number | Date of First Dose | Date of Last Dose | Total Doses Applied | Compliance (%) |
|---------------|-----------------------|---------------------------|--------------------------|----------------------------|-----------------------|
| Cohort 1 | xxxx | yyyy-mm-dd | yyyy-mm-dd | xx | xx.x |

Cohort 2
Cohort 3
Cohort 4

Note to programmer:

Compliance = [Total number of applications] / [Planned number of applications] * 100%, where Planned number of applications is determined as follows:

for subjects who completed the study successfully: 56 applications (28 days of twice daily dosing);

for subjects who discontinued early: the minimum between 56 and [(Date of Discontinuation – Date of First Application)].

Created on: ddmmmyy hh:mm

Page 1 of N

L16.2.5.2 Listing of Study Medication Weight

| Cohort | Patient Number | Bottle 1 | | Bottle 2 | | Total Amount Applied (g) |
|----------|----------------|----------------|----------------------|----------------|----------------------|--------------------------|
| | | Date Dispensed | Weight Dispensed (g) | Date Collected | Weight Collected (g) | |
| Cohort 1 | xxxx | yyyy-mm-dd | xx | yyyy-mm-dd | xx | xxx |

Cohort 2

Cohort 3

Cohort 4

